7.5 Experimental design

Acute pain will be induced through electrical stimulation in an established model first described by [name] et al.[16]. (For detailed experimental setup cp. Chapter 7.6-7.7)

Before the first intervention participants will be randomized to:

- 1) A placebo education group
- 2) A non-placebo education group

Participants in both groups will undergo the pain model two times. Every participant will receive treatment as follows in a sequential cross-over design (cp fig. 1).

[figure not shown]

Figure 1: Experimental design

During every experiment levels of saliva cortisol levels are collected at baseline, 30min, 60min and 100min after pain induction (cp. Fig. 4).

A washout period of two weeks well be instituted to prevent contamination (cp. Fig 1).

Randomization as well as preparation and application of the hidden and not hidden study medication will be executed by study stuff not involved in assessments during the intervention. During the individual experiment pain scores, hyperalgesia and allodynia will be assessed and documented by an investigator blinded to the treatment group.

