The duration of the study from the first participant in to the last participant out is 5 months. Duration of an individual participant from T0-T2 (cp. figure 1) will be approximately 2-3 weeks weeks (time from primary assessment with 1st intervention until 2nd intervention).

[figure not shown]

Figure 1: Study time course for a participant. T= time point

Visit	Description	Involved stuff	Duration	
Inclusion/ Randomization/ Education	 Check of inclusion/ exclusion criteria Discussion of open questions prior to study inclusion Obtain written consent Randomization to PEG or nPEG Placebo education depending on randomization 	 Study nurse Investigator not involved in treatment interventions 	Administrative tasks: 30min Placebo education 10-15min	
1 st intervention	 Treatment A-B depending on randomization Application of open label placebo in treatment B (study nurse; investigator not present) Assessment of outcomes (investigator) 	Study nurseInvestigator	Preparation time: 30 min Intervention time: 100 min	
2 nd intervention	 Second treatment (i.e. treatment B if treatment A applied in 1st intervention). Application of open label placebo in treatment B (study nurse; investigator not present) Assessment of outcomes (investigator) 	Study nurseInvestigator	Preparation time: 30 min Intervention time: 100 min	

Table1: Overview of interventions, involved study stuff and time course

1. Administrative structure:

1.1 Sponsor:

Department of Anaesthesia, Surgical Intensive Care, Prehospital Emergency Medicine and Pain Therapy of the University Hospital Basel

1.2 Sponsor investigators:

[name], PD
Head of Pain Unit
Department of Anaesthesiology/ Chronic pain Unit
[name]
[name] CH
[contact]

E-mail: [contact]

1.3 Principal Investigators:

[name] Senior physician Department of Anaesthesiology/ Chronic pain Unit [name] [name] CH

[contact]

E-mail: [contact]

[name], MSc Research Fellow, Department of Anaesthesiology University of Basel (USB) [name] [name] CH

[contact]Fax: [name] E-mail: [contact]

[name], PD Senior Physician Department of Anaesthesiology University of Basel (USB [name] [name] CH [contact]

[contact]

E-mail: [contact]

[name]

Scientific assistant, doctoral candidate

Department of Anaesthesiology University of Basel (USB)

[name] [name] CH [contact] [contact]

E-mail: [contact]

[name], [name] 1 [name]

[contact] [contact]

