7.4 Participant education in in the placebo education group

The participants randomized to the PEG will receive additionally an education about placebos prior to the first intervention with following content (adopted from prior open label placebo studies [1, 2] and adapted to the current study design):

- A) Showing data about the possible strength of a placebo effect. Abstracts of prior placebo investigations are presented [1, 2].
- B) The possible automatically response of the body to placebo application is discussed. Pavlov dogs experiments and effects of prior studies are presented to the volunteer.
- C) Education that a positive attitude towards placebos can be helpful but is not necessary for the placebo effect [8-10].
- D) A television news report of an open label placebo education is shown to the participant at the end of the education session. (excerpted from: http://www.nbcnews.com/video/nightly-news/40787382#40787382). To ensure proper understanding we add a German subtitle to the original report (English).

The education is done via a slide show, performed exactly the same in every volunteer. The duration of the presentation is about 10 minutes. (Slides are attached at the appendix of this protocol.) The investigator of the treatment interventions is not involved in placebo education prior to intervention.

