7.10 Open label placebo application

Open-label placebo is given during Treatment B. A pain expert of the study stuff (the same person for one participant during the two interventions) applies placebo in treatment B. For an open-label placebo application the volunteer is orally informed that he will receive an intravenous placebo ("medical" not active substance) now. To strengthen positive expectations the study nurse assures the patient that placebos can have a strong effect on pain before application of the syringe content. The placebo is then injected intravenous while the investigator ensures that the volunteer watches the injection. The oral information text is standardized is exactly the same in every participant. (For the orginal text in german language cp. appendix)

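### The person who delivers the placebo is not stated to be blind to education group, and the plan disagrees on who that person is, so the secondary education comparison is open to performance bias

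*Combined protocol and SAP*

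**What the plan says.** On who randomises and who delivers:

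- Section 7.5 gives both tasks to one class of staff, defined only as having no part in the assessments: "Randomization as well as preparation and application of the hidden and not hidden study medication will be executed by study stuff".
- The visit overview table under Study schedule (the first of two tables numbered 1) lists two roles at the visit for inclusion, randomisation and education: a study nurse, and an "Investigator not involved in treatment interventions". For both pain sessions it then reads "Application of open label placebo in treatment B (study nurse; investigator not present".
- Section 7.10 names two roles. First, "A pain expert of the study stuff (the same person for one participant during the two interventions) applies placebo in treatment B". Then, "To strengthen positive expectations the study nurse assures the patient that placebos can have a strong effect on pain".
- The Appendix attributes the script to the assessor and adds that one person always delivers it.

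On blinding and separation:

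- Section 7.4: "The investigator of the treatment interventions is not involved in placebo education prior to intervention". The study nurse is not mentioned.
- Section 7.11 blinds the testing investigator to whether A or B is given. It describes one randomisation code, locked away, with access limited to staff who plan the interventions. It does not separate the education list from the A/B list.

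On standardisation: section 7.10 and the Appendix fix the wording. The Appendix also prescribes the speaker's position, tone of voice and a slow, visible injection.

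**The concern.** Saline is inert, so what the deliverer says and how it is said is the treatment. Section 3 itself names clinician communication and trust among the determinants of the placebo response. If the deliverer knows who has been educated, tone, conviction or unscripted talk could differ between the education groups. If the deliverer also took part in the teaching, educated participants would have had more prior contact with that person.

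B1 versus B2 compares different participants on self-reported pain, so the crossover does not cancel a difference of this kind. Blinding the assessor does not remove it either, because it enters at the injection. It could then not be told apart from an effect of the educational content, which is the first secondary objective and the reason for the second randomisation.

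**Working it through.** The plan gives no figure for this point, so the first step is to set the sections side by side.

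1. **Does one role cover both tasks?** Yes. The study nurse is listed at the randomisation and education visit and named as giving the placebo at either session. Section 7.10 has the nurse speak the suggestion. Section 7.5 is consistent with this, since it separates these staff only from assessment.
2. **Does one individual do both?** Not stated. The overview table lists roles per visit and does not say who performs which task at the first visit.
3. **Who delivers?** Unresolved: study nurse (overview table), pain expert who applies and study nurse who speaks (7.10), assessor (Appendix). Read literally, the Appendix would also conflict with 7.11, where the tester leaves the room before any placebo is given.
4. **Is the deliverer blind to education group?** No section says so. 7.11 covers the tester and A versus B. 7.5 covers the assessor. 7.4 covers the investigator of the treatment interventions.
5. **Which comparison is exposed?** Section 11.4 compares AUPC under B1 with AUPC under B2, in different participants. The primary B versus A contrast is within participant and does not depend on the deliverer knowing the education group.

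The second step illustrates what a delivery difference could do to the B1 versus B2 test.

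- From section 11.2: SD of AUPC = 1 NRS × 60 min = 60 NRS-minutes, which reproduces the plan's value. The 60 minutes are minute 40 to 100, as in sections 5.1 and 11.1.
- Assumed: 32 participants split 16 and 16, no true education effect, a two-sided 5% two-sample test in normal approximation, and a delivery bias of *b* NRS-minutes. The documents support no particular *b*.
- Standard error = 60 × √(2/16) = 21.2.
- False-positive rate = Φ(−1.96 + b/SE) + Φ(−1.96 − b/SE).

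| b (NRS-minutes) | b/60 (NRS points) | b/SE | False-positive rate |
|---|---|---|---|
| 0 | 0 | 0 | 5.0% |
| 5 | 0.08 | 0.24 | 5.6% |
| 10 | 0.17 | 0.47 | 7.6% |
| 20 | 0.33 | 0.94 | 15.6% |
| 30 | 0.50 | 1.41 | 29.3% |

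With 14 per group, SE = 60 × √(2/14) = 22.7, and the rates for 5, 10, 20 and 30 are 5.6%, 7.3%, 14.3% and 26.3%. A small bias does little; one of a third to half an NRS point would matter.

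**The case against.** A reader might infer that the people who randomise and educate are the same people who speak and inject, and therefore know each participant's group. The documents do not support that. They show overlap of role, and the pain-expert sentence in 7.10 points to someone else. At the first visit the nurse may handle only administration, while the listed non-treatment investigator gives the slide show.

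Section 7.4 may also reach further than the tester. Section 7.10 has an investigator make sure that the volunteer watches the injection, at a moment when the tester is out of the room, so the word is not reserved for the tester.

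The safeguards are real. The words are fixed, the manner is prescribed, one person always speaks, and access to the code is restricted. The direction of any bias is not given either: a deliverer who knows the group could try harder with uneducated participants. Finally, participants can disclose their education at the bedside, so no staffing rule guarantees blinding.

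Most of this stands, and it narrows the point. It does not remove it:

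- A script and a single speaker remove differences in wording and between speakers. They do not stop one speaker who knows the group from behaving differently by group.
- Someone present at the education visit does not need the code.
- The ambiguity in 7.4 and 7.10 is itself a reason to state who delivers and what that person knows.

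**Conclusion.** The concern holds in a limited form. By role, the study nurse is at the randomisation and education visit and later speaks the suggestion and gives the placebo. The deliverer is not stated to be blind to education group, and the staffing table makes knowledge of it likely. The plan also contradicts itself on who delivers.

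The exposure is confined to non-verbal or unscripted behaviour and prior rapport, and to the secondary B1 versus B2 comparison. Its size and direction are unknown. The rates of 5.6% to 29.3% rest on assumed biases, equal groups of 16 and the plan's SD; they show sensitivity and do not estimate a bias. Two stronger conclusions are not supported: that performance bias in favour of education is established, and that the primary B versus A result is affected. This is an inexpensive improvement that should be made.

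**What to change.** - Reconcile the visit overview table, 7.5, 7.10 and the Appendix, so that one named role speaks the script and injects.
- Assign allocation to education or no education, and the slide show, to the non-treatment investigator already listed in the overview table.
- State that the person who speaks and injects does not attend that part of the visit. That person should receive only a session list showing A or B, kept apart from the education list. Amend 7.11 to describe the two lists.
- If separation is not possible, record the deliverer's guess of education group for each participant and report the lack of blinding as a limitation of B1 versus B2.

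The cost is a second list and less flexible rostering of the study nurse. The documents give no staffing numbers, so whether this can be done entirely with present staff is for the sponsor to confirm. Participants may still reveal their group, so the change lowers the risk but does not remove it.

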7.6 Experimental setup

Every participant will be intensive familiarized with the pain scale, the intradermal electrical stimulation model evoking pain, hyperalgesia and allodynia examination. A training session would be rather invasive and includes the risk of habituation and is therefore not applied. Previous studies conducted by our research group using this model have also shown that this is not required.

The model we use in this study was first described by [name] at al.[16]. It has been used in numerous studies investigating pain, pain medications, hyperalgesia and allodynia [26-31]. Our utilized pain model has been shown to provoke stable areas of secondary hyperalgesia

to pinprick and touch caused by an activation of mechanoinsensitive C-nociceptors [32] (a class of nociceptors shown to be activated electrically, preferentially at high current densities, as used in this model [33, 34]).

7.7 General setup of intradermal electrical stimulation (cp. Figure 3)

Two microdialysis catheters with internal stainless steel wires are inserted in parallel into the intradermal, volar surface of the contralateral forearm for a length of approximately 10mm and are separated 5mm from each other. The catheters are filled with 0.9% saline and a continuous flow of 0.2µl/min ensured by a syringe pump (Perfusor®) to facilitate conduction. The stainless steel wires are attached to a constant current stimulator (manufactured by [name] et al.) and monophasic, rectangular electrical pulses of 0.5ms duration are applied with alternating polarity at 2 Hz. The current will be increased to target a pain rating of 6 of 10 on a numeric rating scale (NRS) (0= no pain and 10 maximum tolerable pain). Three further increases in current will be made every 5 min for the next 15min to compensate for habituation. This final current will be kept constant until the end of the particular experiment (100min cp. figure 4). After calibration to NRS 6 there is no further increase of the current.

7.8 Procedures/ Recordings/ Interventions before and during electrical stimulation

Measurement of pain:

After adjusting for habituation as delineated above, pain, hyperalgesia, and allodynia will be assessed every ten minutes after time-point for possible OLP-application, using the NRS until the end of the individual session after 100 minutes (cp.Figure 4).

Measurement of hyperalgesia and allodynia:

Immediately after every pain rating the area of pinprick hyperalgesia is determined using a 256 mN von Frey filament and allodynia is determined using a dry cotton swab. Measurements are conducted from a more distant to a more central site along four orthogonal lines (distal, proximal, lateral, and medial) that will be drawn onto the skin with tick marks indicating each centimetre (cp. picture 1). Distal and proximal measurements will begin 12cm from the site of electronical stimulation; whereas the lateral and medial measurements were begin 6cm from this site. In both cases the used filament will be moved towards the site of stimulation in 0.5 cm increments until the subject reports either increased pain sensations from the von Frey filament (hyperalgesia) or an unpleasant "rougher" sensation from the cotton swab (allodynia). To create an area from these linear measurements, the assumption is made, that this field has the shape of an ellipse. The area is calculated using the formula $1/4\pi D \cdot d$.

Pain, hyperalgesia and allodynia measurement are exactly the same in both experimental interventions.

Picture 1: A: microdialys catheter inserted intra-cutaneous at the forearm; B: testing hyperalgesia with 256 mN von Frey filament; C: testing allodynia with a cotton swap.; adopted with permission from Mauermann et al., Anesthesiology, 2016. 124(2): p. 453-63.

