- To investigate the effect of education prior to an open label placebo application.
- To investigate the effect of open label placebo application on biomarkers of stress (saliva cortisol)

Outcome(s):

[figure not shown]
Primary outcome:

Pain response measured by the Area under the Pain Curve (AUPC) using the numeric rating scale (NRS) from minute 30 to 100 after inducing definded pain in an experimental setting. Main comparison: The effect of open label placebo v.s. no treatment intervention.

Secondary outcomes:

 The pain response measured by the AUPC (NRS every 10 minutes during electrical stimulation) will be used for further comparison of the two different treatment interventions every participant recieves during the study.

	 Regularly taking medication potentially interfere with pain sensitation (analgesics, antihistamines and calcium and potassium channel blockers) Neuropathy Chronic pain Neuromuscular or psychiatric disease Known or suspected kidney or liver disease 		
Measurements and procedures:	Healthy male adults are recruted via an advertisment on the homepage of the University of Basel. After informed consent, but before any intervention, the participiants are randomized to a placebo educated and a non-educated group. The education group will receive an education about placebos and their effects prior to study intervention during the placebo will be applied. Every participiant will pass trough two interventions with electrical induced pain, defined at a NRS of six for 100 minutes each. Between the sessions a minimal two weeks washout period will be hold. During the two interventions participiants beceive the following treatments delineated above in a randomized manner.		
Study medication/ Study product:	Intravenous application of: open label placebo (2ml saline 0.9%).		
Control intervention	During one intervention (A) we do not apply any treatment at all during the intervention time. This to control for habitation effects during current application and create a comparison.		
Number of Participants with Rationale:	Based on our sample size calculation, we will require 22 participants. Recent estimates state that some 20-30% of patients are placebo-non-responders. Consequently, we will include 29 patients. However, with an estimated drop-out of 10% we plan to recruit 32 paitents. Patients dropping out will be replaced.		

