5.2 Secondary outcomes

- The pain response measured by the AUPC (NRS every 10 minutes during electrical stimulation) will be used for further comparison of the two different treatment interventions every participant recieves during the study. We compare the participants received a education about placebo to the non prior educated participants.
- 2. Hyperalgesia and allodynia will be measured analogously to the NRS as above.
- 3. Saliva concentration of cortisol, measured at baseline, 30, 60 and 100 minutes after pain induction.

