11.2 Determination of sample size

Sample size has been determined by a Wilcoxon signed-rank test for the AUPC for Treatments A and B. The AUPC is the product of the NRS x Time. 7 measurements of NRS will be made in total, one every ten minutes. We expect the area under the curve to be 50 NRSxminutes based on a general difference of 1 NRS point and some time for the effect to fully develop. We expect the standard deviations in both groups to be 1 NRS or 60 NRS*min. Using a t-test with a 20% mark-up for non-parametric data we have arrived at a required number of patients of 22. However since 20-30% of participants can be expected to be non-responders to placebo [38] and expecting 10% drop out we have arrived at a total number of patients to be recruited of 32.

11.3 Statistical criteria of termination of the trail:

Upon completion. With such a small sample size, no interim analysis will be conducted.

11.4 Planned Analyses, Datasets, and Analysis Populations:

For the first hypothesis (AUPC for $B_{1/2}$ vs. A) we will conduct a Wilcoxon signed-rank test. Additionally, we conduct a mixed effects model using the AUPC as the dependent outcome and the treatment, the session order (e.g. Treatment B before Treatment A) time during electrical stimulation (in minutes), and finally the individual. This will allow for a more differentiated analysis accounting for temporal and sessional habituation in explaining the treatment effect.

For the effect of education, we will compare the AUPC of: Treatment B_1 vs Treatment B_2 , again by a Wilcoxon signed-rank test.

The outcomes hyperalgesia and allodynia, as well as biomarkers will be examined analogously to the respective comparisons with the AUPC.

11.8 Interim analysis:

Given the small sample size and limited time, no interim analysis will be conducted.

11.9 Safety analysis:

None. However, patients will be under the continuous surveillance of anesthesiology staff.

11.10 Deviation(s) from the original statistical plan:

The statistical plan will be published prior to commencement on clinicaltrials.gov. Any deviations from the statistical plan will be reported and justified in the final report.

11.11 Handling of missing data and drop outs:

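### No planned analysis uses the pain rating just before the placebo time-point, which may differ between a participant's two sessions; the cost is precision, not bias

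*Combined protocol and SAP*

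**What the plan says.** **When pain is rated.** Section 7.8 states that pain "will be assessed every ten minutes after time-point for possible OLP-application". Section 5.2 describes the secondary AUPC as "NRS every 10 minutes during electrical stimulation", which would include ratings before placebo. The synopsis defines the primary AUPC "from minute 30 to 100 after inducing definded pain", whereas 5.1 and 11.1 use minutes 40 to 100. Section 11.2 counts seven ratings, which fits 40 to 100; a 30 to 100 window would have eight. Figure 4, the session schedule, is not available here and may settle the point.

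**How pain is set.** Under 7.7 the current is titrated to NRS 6, raised three more times over 15 minutes against habituation, then held constant. Under 7.9 placebo is given 30 minutes after calibration.

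**What is analysed.** In 11.4 the primary comparison (B versus A) is a Wilcoxon signed-rank test on the AUPC. In addition, "we conduct a mixed effects model using the AUPC as the dependent outcome", with treatment, session order, minutes of stimulation and individual as terms. No baseline, change score or covariate is defined.

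**The concern.** Each session has its own titration, and from then on the participant's pain drifts under a fixed current. If calibration is counted from first reaching NRS 6, the last current increase comes 30 − 15 = 15 minutes before placebo; if counted from the last increase, the gap is 30 minutes. The plan treats habituation as real: it cites habituation as a reason for the no-treatment session, for randomising the order, for having no training session, and for fitting the mixed model.

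A participant could therefore reach the placebo time-point at a different pain level in each session, for reasons unrelated to placebo. That difference passes into his B minus A difference in AUPC. A session-order term removes only the average shift between first and second sessions, not one person's deviation from it. The time term cannot help either: with the AUPC as dependent variable there is one value per session, so minutes of stimulation do not vary within it. At stake is the precision of the primary treatment estimate in a small trial.

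**Working it through.** **Inputs**
- Effect (11.2): "We expect the area under the curve to be 50 NRSxminutes based on a general difference of 1 NRS point".
- SD (11.2): "We expect the standard deviations in both groups to be 1 NRS or 60 NRS*min". This is a per-condition SD, not the SD of the B minus A difference.
- Not stated: alpha, sidedness, power, within-person correlation ρ. Assumed: two-sided 0.05, power 80% or 90%, ρ from 0 to 0.7.
- Not stated: r, the correlation between the B minus A difference in pre-placebo NRS and the B minus A difference in AUPC. Assumed 0 to 0.7.
- Window: minutes 40 to 100, i.e. 60 minutes.

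**Step 1: the plan's own figure.** Section 11.2 says: "Using a t-test with a 20% mark-up for non-parametric data we have arrived at a required number of patients of 22". With SD of the difference = 60·√(2(1 − ρ)), an exact paired t-test for a difference of 50, and the result × 1.2 rounded up:

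| ρ | SD of difference | n at 80% → ×1.2 | n at 90% → ×1.2 |
|---|---|---|---|
| 0 | 84.9 | 25 → 30 | 33 → 40 |
| 0.3 | 71.0 | 18 → 22 | 24 → 29 |
| 0.5 | 60.0 | 14 → 17 | 18 → 22 |
| 0.7 | 46.5 | 9 → 11 | 12 → 15 |

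The 22 is reproduced at ρ = 0.3 with 80% power and at ρ = 0.5 with 90% power. The plan does not say which, if either, was meant. The SD of the difference equals 60 only at ρ = 0.5.

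**Step 2: gain from adjustment.** Residual variance = (1 − r²) × variance of the difference, so the effective sample multiplier is 1/(1 − r²). The multiplier depends on r alone. The last three columns also need SD of the difference = 60 (ρ = 0.5); n is for 90% power with the 20% mark-up, and about one more is needed for the lost degree of freedom.

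| r | Multiplier | Residual SD | n | Simulated power at n = 22, adjusted |
|---|---|---|---|---|
| 0 | 1.00 | 60.0 | 22 | 0.95 |
| 0.3 | 1.10 | 57.2 | 20 | 0.97 |
| 0.5 | 1.33 | 52.0 | 17 | 0.98 |
| 0.7 | 1.96 | 42.8 | 12 | above 0.99 |

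In the same simulations (3,000 trials per row) the unadjusted Wilcoxon test had power of about 0.95 in every row. Type I error was close to 5% for both methods (0.044 to 0.061).

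**Step 3: what r might be.** If a pre-placebo difference persists in full over the window, each NRS point shifts the AUPC by 60 NRS·min: 0.25, 0.5 and 1 point give 15, 30 and 60, or 30%, 60% and 120% of the planned 50. If these differences have SD s across participants and the rest of the AUPC difference is independent of them, r = 60s / SD of difference. For s = 0.5 (assumed) this is 30/60 = 0.50, 30/71.0 = 0.42 and 30/84.9 = 0.35 at ρ = 0.5, 0.3 and 0.

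**Step 4: chance imbalance.** With n = 22 and full persistence, the mean imbalance has SE 60s/√22. That is 6.4 NRS·min at s = 0.5 (95% range ±12.5) and 12.8 at s = 1 (±25.1). This is part of the planned standard error, not an addition to it. At ρ = 0.5 the case s = 1 would use up the whole SD of 60, so it is a limit.

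**Step 5: covariate or subtraction.** Subtracting the baseline can lose precision. With r = 0.3, SD of difference 60 and a baseline difference of SD 1 NRS (60 NRS·min over the window), the SD becomes √(60² + 60² − 2 × 0.3 × 60 × 60) = 71.0, and n rises from 22 to 29. Covariate adjustment cannot do worse than one lost degree of freedom.

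**The case against.** The strongest reply is that the unadjusted crossover comparison is already valid. Order is randomised, every participant has a no-treatment session, and titration to NRS 6 with three compensating increases is meant to equalise sessions. The better that works, the less a baseline can explain; at r = 0 it explains nothing. This stands. A reader might infer that habituation biases B against A, or that pain at the placebo time-point is known to differ between sessions. The documents support neither: randomised order leaves only chance differences, and no data on pain at that time-point are reported.

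Second, the primary test is the Wilcoxon test, and a covariate in the mixed model does nothing for it. This also stands. A reader might take the multipliers as a gain in the primary test, or as evidence that 22 is too few. They are neither: with SD of the difference 60 and the planned effect, the unadjusted test already has power of about 0.95 at n = 22.

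Third, the baseline may not be wholly free of treatment influence. Under 7.3 every participant knows that he gets placebo in one session and nothing in the other, so in session 2 he can infer what is coming. As an assumed illustration, suppose that awaiting placebo lowers the session-2 baseline by 0.5 NRS in sequence A then B only. The mean B minus A baseline difference is then −0.25. At a slope of 30 NRS·min per point, adjustment moves the estimate by 0.25 × 30 = 7.5 NRS·min, or 15% of 50. So the covariate cannot be called unbiased without qualification. This is a reason to report both results, not to omit the adjusted one.

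Finally, the rating may simply not be collected. That changes the remedy slightly, but not the absence of a baseline from 11.4.

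**Conclusion.** The point holds as one of precision. No analysis in 11.4 uses a pre-placebo NRS, and the order and time terms cannot stand in for it. The documents also disagree on whether a rating at minute 30 is taken and, under the synopsis window, would put it inside the outcome.

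The effective sample multiplier is 1.00, 1.10, 1.33 or 1.96 at r = 0, 0.3, 0.5 or 0.7, where r is assumed throughout. The residual SDs of 57, 52 and 43 hold only if the SD of the difference is 60, i.e. within-person correlation 0.5, which the plan does not state. The gain applies to the mixed-model estimate of B versus A only. The change is worth making because it is cheap and serves the mixed model's stated purpose of accounting for habituation, not because the planned test is invalid.

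**What to change.** 1. Reconcile the synopsis, 5.1, 5.2 and 7.8 on the primary window and on whether a rating is taken at minute 30.
2. State in 7.8 that an NRS is recorded in both sessions immediately before the possible placebo time-point and before any announcement of placebo. The blinded assessor can take it before leaving the room (7.11). Section 7.12 already schedules a saliva sample at that stage, before application.
3. Keep this rating out of the AUPC.
4. In 11.4, prespecify it as a session-level covariate, not a subtraction, in the mixed model for B versus A. Entering it as the deviation from the participant's own two-session mean makes the slope a within-person one, which is what r describes. Do not extend it by default to the education comparison, because education is given before the rating and could affect it.
5. Keep the unadjusted Wilcoxon test as planned and report the two results side by side.

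Cost: one spoken rating per session, if not already taken, and one degree of freedom. The remaining downside is that the session-2 baseline may carry some anticipation; the unadjusted result lets readers check whether this matters.
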